6.1 Basic Definitions

Investigational Product (IP)

Romosozumab or placebo.

Interactive Voice Response System (IVRS)

The system used to assign eligible subjects to randomized treatment as well as to manage IP supply at the site and track subjects' study termination data.

6.2 Study Points of Reference

Baseline

The baseline measurement is defined as the last measurement prior to the first dose of IP. If the measurement is taken on the same day as the first dose and the exact measurement time relative to the first dose is unknown, it will be assumed to have been taken prior to the first dose of IP. If a subject does not receive IP baseline is the closest recorded measurement on or prior to the randomization date. For baseline duplicate BMD, the baseline is obtained as the average of the measurements taken prior to the first dose of IP.

Study Day 1

The first day of IP administration or the day of randomization for subjects who do not receive any dose of IP.

Study Day

The number of days from Study Day 1, inclusive:

$$\text{Study Day} = (\text{Date of Interest} - \text{Date of Study Day 1}) + 1.$$

Analysis Visit Windows

Based on protocol, all monthly study visits up to month 5 have a -/+7 day window. The study visits at month 6 and month 9 have a -7/+ 3 day window. Study procedures for a specific visit may be completed on multiple days as long as all the procedures are completed within the visit window. To allow for variations in scheduling study visits, the analysis visit windows defined in [Appendix 13.1.2](#) will be used to assign evaluations to the most appropriate nominal visit for analysis and summarization.

6.3 Study Dates

Informed Consent Date

The date on which a subject signs the informed consent.

Screening Date

Screening date is defined as the date of the first screening visit if there is more than one screening visit.

Enrollment (Randomization) Date

The date on which a subject is assigned to one of the treatments through the IVRS.

First Dose Date

The date of administration of first dose of IP; this date may or may not be the same as the randomization date.

Last Dose Date

The date of administration of last dose of IP.

End of Study Date

End of study date is defined as the date of the last assessment for the Month 9 visit for subjects who completed the study; or the date of the last assessment for the early termination visit for subjects who discontinued the study.

End of 6-Month Treatment Period Date

End of treatment period date is defined as the date of the last assessment of Month 6 visit. For subjects who discontinued from the study before completing Month 6 visit, the end of study date is used for the end of treatment period date. For those subjects who

missed Month 6 visit and did not early terminate, the target day (Day 183) for Month 6 plus 3 days will be used as the end of treatment period.

Start of Follow-up Period Date

End of 6-month treatment period date plus one day.

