6.4 Study Time Intervals

Screening Period

The time period between the date of informed consent and first dose of IP or randomization date for subjects who do not receive IP.

Treatment Period

The time period from the first dose date to the end of 6-month treatment period date inclusive.

Follow-up Period

For subjects entering in the 3-month follow-up period: the time period from the start of follow-up period date to the end of study date.

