10.7.1 Adverse Events

The Medical Dictionary for Regulatory Activities (MedDRA) version 20.0 or later will be used to code all AEs to a system organ class and a preferred term. AEs will be summarized in the 6-month treatment period and in the 9-month study period for all subjects who receive at least one dose of IP in the treatment period, ie, safety analysis

set. The subject incidence rates for the 9-month study period will include all events that occurred in the 6-month treatment period, and in addition, all events that occurred in the additional 3 month follow-up period. In addition, AEs reported between month 6 and month 9 (no treatment phase) will be listed by subject number and treatment received in the first 6 months.

All AE tables will be summarized by treatment group. The subject incidence of AEs will be summarized for all treatment emergent, serious, treatment related, serious treatment related, leading to withdrawal of IP, fatal, and of special interest. Subject incidence of special interest adverse events will also be summarized according to their categories.

Subject incidence of all treatment emergent, , serious, those leading to withdrawal of IP, related to IP adverse events will be tabulated by system organ class (SOC) and preferred term in descending order of frequency in the romosozumab arm. Fatal adverse events will be tabulated by preferred term in descending order of frequency in the romosozumab arm.

Disease related events (DRE) will be indicated in the AE listing and only tabulated with sufficient data.

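### SAP 6.3 does not cap the 6-month treatment period for a woman who misses Month 6 and then withdraws during follow-up, so later adverse events can enter the 6-month safety tables

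*SAP*

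**What the plan says.** SAP Section 6.3 sets the end of the 6-month treatment period by three rules.

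- **Rule A**, Month 6 visit completed: "End of treatment period date is defined as the date of the last assessment of Month 6 visit".
- **Rule B**, left the study: "For subjects who discontinued from the study before completing Month 6 visit, the end of study date is used".
- **Rule C**, for those who "missed Month 6 visit and did not early terminate, the target day (Day 183) for Month 6 plus 3 days will be used".

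For a woman who discontinues, the same section takes the end of study date from her early termination (ET) visit: "or the date of the last assessment for the early termination visit for subjects who discontinued the study". Follow-up starts at "End of 6-month treatment period date plus one day". SAP Section 6.4 defines the treatment period as "The time period from the first dose date to the end of 6-month treatment period date inclusive" and runs follow-up from its start date to the end of study date.

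SAP Section 10.7.1 tabulates adverse events for the 6-month treatment period and for the 9-month study period. It adds a separate listing: "AEs reported between month 6 and month 9 (no treatment phase) will be listed". Protocol Section 10.5.5.1 plans the same listing.

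**The concern.** Rule C shows the intent: a missed Month 6 visit should not stretch the treatment period beyond Day 186. Its condition on early termination removes that limit for a woman who misses Month 6, remains in the study and withdraws some time before Month 9. Two women with the same dosing and the same missed visit then get treatment periods of different length, only because one of them later withdrew.

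The 6-month incidence of adverse events is a listed safety endpoint (SAP Section 4.1.4), and so is the 6-month incidence of adjudicated positive cardiovascular serious adverse events. Protocol Section 9.2.2.1 collects events through the end of study or ET visit, so events after Day 186 will be in the database and must be assigned to a period. Under Rule B they go to the treatment period, although both documents describe Months 6 to 9 as free of treatment.

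**Working it through.** **Inputs.** Month 6 target Day 183 and Month 9 target Day 275 (SAP Appendix 13.1.2). Visit window of -7/+3 days at Months 6 and 9 (SAP Section 6.2). About 30 women per arm (SAP Section 3.1). Last scheduled dose at Month 5 (protocol Section 6.2.1.1), taken here as about Day 153, which is an assumption. The sample size calculation does not enter this point.

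**The plan's own limit.** 183 + 3 = Day 186.

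**Which rule applies.** Let E be the study day of her ET visit, with E > 186. Rule A fails because she did not complete Month 6. Rule C fails because she did terminate early. Rule B fits and gives Day E.

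**Overrun.** Days beyond the limit = E - 186.

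| ET on day | End under Rule B | End if capped | Overrun (days) | Days after Month 5 dose (E - 153) |
|---|---|---|---|---|
| 187 | 187 | 186 | 1 | 34 |
| 200 | 200 | 186 | 14 | 47 |
| 230 | 230 | 186 | 44 | 77 |
| 260 | 260 | 186 | 74 | 107 |
| 267 | 267 | 186 | 81 | 114 |
| 274 | 274 | 186 | 88 | 121 |

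Day 274 is the day before the Month 9 target: 88/186 = 47%. If any visit inside the Month 9 window counts as Month 9, the window opens on 275 - 7 = Day 268. The latest withdrawal is then Day 267: 81/186 = 44%.

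**Follow-up period.** It starts on Day E + 1 and ends on Day E, so its length is E - (E + 1) + 1 = 0 days. With the cap it would run from Day 187 to Day E.

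**Primary against final analysis.** Suppose she is still in follow-up when the data for the primary analysis are cut. She has not terminated, so Rule C gives Day 186. If she then withdraws, Rule B gives Day E at the final analysis, which repeats the 6-month safety endpoints (SAP Section 6.7.2). An event between Day 187 and Day E would be added to a 6-month table already produced.

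**Effect on incidence.** One woman in 30 is 1/30 = 3.3 percentage points. This is the most she can add to any one event, and only if the event is new for her after Day 186.

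**Frequency.** The documents give no rate for this sequence. The 10% dropout in SAP Section 3.2 is a power assumption covering all reasons: 0.10 x 60 = 6 women. Those who miss Month 6, stay on and then withdraw are a small part of that, probably 0 to 1. This is a judgement, not a figure from the plan.

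**The case against.** The strongest reply is that Rules B and C are a pair. On that view Rule B concerns women who leave before the Month 6 time point, and Rule C's condition means not having left in that way. A woman who withdraws in follow-up then falls under Rule C and stops at Day 186. SAP Section 6.4 lends some support, since it defines follow-up for those who enter it and an empty follow-up period looks unintended.

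This is a fair account of what was probably meant, but it needs words that Rule C lacks. Rule C excludes early termination without limiting when it happened. Reading only Rule B as a statement of timing leaves her under no rule, with an undefined date. Treating her ET visit as the Month 6 visit, which the shared column in protocol Table 1 and the combined visit in protocol Section 7.2.3 invite, brings her under Rule A and gives the same late date.

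The reply is right on scale. The safety analyses are descriptive, the sequence is rare, and all her events are in the 9-month tables either way.

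Two stronger inferences are tempting and do not hold. A reader might conclude that her events also disappear from the Month 6 to 9 listing. SAP Section 10.7.1 and protocol Section 10.5.5.1 define that listing by calendar months and not by the derived follow-up period, so an event on Day 230 stays in it. A reader might also take Day 275 as the limit of the overrun, but a woman assessed on that day is at her Month 9 visit and has not withdrawn before it.

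**Conclusion.** The rule is wrong as worded, with small consequences. For a woman who misses Month 6 and withdraws during follow-up, the treatment period can overrun Day 186 by up to about 88 days, or about 81 if the Month 9 window is respected, and her derived follow-up is empty. Events up to about 121 days after the last scheduled dose could be counted as treatment-period events, assuming that dose falls near Day 153. The same 6-month table could also change between the two analyses.

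The effect is limited to the descriptive 6-month adverse event tables and arises only if she has an event after Day 186. The BMD analyses do not use this date. The point merits a clarification before database lock; it does not threaten the trial's conclusions.

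**What to change.** Replace Rule B in SAP Section 6.3 with wording to this effect: *a woman who leaves the study without completing the Month 6 visit has her treatment period ended on the earlier of her end of study date and Day 186; an ET visit after Day 186 is not treated as the Month 6 visit for this date.*

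The second clause is needed because Rule A could otherwise return the late ET date. Limiting it to this date leaves the visit windows in SAP Appendix 13.1.2 alone, so a DXA scan at a late ET visit is still assigned to Month 6 as planned.

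Women who withdraw by Day 186 keep the same date, and the follow-up definition in SAP Section 6.4 then works unchanged. The cost is one sentence in the SAP and one line of derivation code, with no change to data collection.

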6.4 Study Time Intervals

Screening Period

The time period between the date of informed consent and first dose of IP or randomization date for subjects who do not receive IP.

Treatment Period

The time period from the first dose date to the end of 6-month treatment period date inclusive.

Follow-up Period

For subjects entering in the 3-month follow-up period: the time period from the start of follow-up period date to the end of study date.

6.5 Subject Disposition

Enrolled (Randomized)

Individuals are considered enrolled if they have been assigned a randomization number. Enrolled individuals are referred to as “subjects”.

Exposed to IP

Subjects are defined as exposed to IP if they have a value for the sum of IP volume that exceeds zero.

6.6 Arithmetic Calculations

Age at Randomization Date

Number of whole years from a subject’s birthdate to the randomization date as recorded on the eCRF.

Estimated Glomerular Filtration Rate (eGFR)

$eGFR(mL/min/1.73 m^2)=175 \times (S_{cr, std})^{-1.154} \times (Age)^{-0.203} \times (0.742 \text{ if female}) \times (1.212 \text{ if African American})$

where $S_{cr, std}$ is serum creatinine in standard unit (mg/mL)

Percent Change From Baseline

The change from baseline value divided by baseline value and multiplied by 100:

$((\text{value at date of interest} - \text{baseline value}) / \text{baseline value}) * 100.$

Subject Incidence for AEs

The subject incidence for a given event in a given time period is defined as the number of subjects with ≥ 1 reported occurrence of the event divided by the number of subjects who are at risk for having the event at the beginning of the given time period. For subjects with multiple occurrences of the same event, the event will only be counted once per subject.

BMD Value for Duplicate Scans

For DXA scans of spine and femur where duplicate measurements are taken, the mean of duplicate records will be used for analysis.

6.7 Study Analyses

6.7.1 Primary Analysis

The analysis of primary, secondary, exploratory, as well as the safety endpoints through Month 6 is considered the primary analysis. The primary analysis will be performed when all subjects have had the opportunity to complete the treatment period (Month 6 visit).

6.7.2 Final Analysis

Final analysis will include the analysis of primary, secondary, exploratory efficacy endpoints, as well as the safety endpoints through 6-month treatment period and the analysis of safety endpoints (adverse events and formation of anti-romosozumab antibodies) for the 9-month study period. The final analysis will be performed when all subjects have completed the 6-month treatment period and the 3-month followup period.

7. Analysis Subsets

7.1 Full Analysis Set

This analysis set includes all randomized subjects. Subjects in this set will be analyzed according to their randomized treatment assignment, regardless of treatment received.

7.2 BMD Efficacy Analysis set

The BMD efficacy analysis will include all randomized subjects who have a baseline DXA BMD measurement and at least 1 post-baseline DXA BMD measurement for the skeletal site (lumbar spine, femoral neck, or total hip) being evaluated. BMD endpoint data from subjects in this set will be analyzed according to randomized treatment groups, regardless of actual treatment received.

7.3 BTM Efficacy Analysis set

The BTM efficacy analysis set will include all randomized subjects who have a baseline measurement and at least 1 post-baseline measurement for the endpoint of interest (CTX, P1NP). BTM endpoint data from subjects in this set will be analyzed according to randomized treatment groups, regardless of actual treatment received.

7.4 Safety Analysis Set

The safety analysis subset will include all randomized subjects who receive at least 1 dose of IP. These subjects will be analyzed according to their actual treatment received, where subjects who receive at least 1 dose of romosozumab will be analyzed in the romosozumab treatment group regardless of the randomized treatment.

7.5 Pharmacokinetic Set

The pharmacokinetic set includes all subjects in the safety set who have evaluable serum romosozumab concentration. This set will be used in all PK analyses.

8. Interim Analysis and Early Stopping Guidelines

No interim analysis is planned for this study.

The primary analysis will occur after all subjects have had the opportunity to complete the Month 6 study visit. The final analysis will be performed after all subjects have had the opportunity to complete the Month 9 end of study visit.

9. Data Screening and Acceptance

9.1 General Principles

The objective of the data screening is to assess the quantity, quality and statistical characteristics of the data relative to the requirements of the planned analyses.

9.2 Data Handling and Electronic Transfer of Data

All data for this study will be received from Amgen's data management department and will be housed within the Electronic Data Capture (EDC) database, Rave. All screening and on-study blood samples will be processed by the central laboratory and will be electronically transferred to the Amgen database. All imaging data will be submitted to the central imaging vendor for analysis. The results from the central imaging vendor analysis will be electronically transferred to the Amgen database. All other data will be captured on the eCRF.

An Analysis Dataset for PK Concentrations (ADPC) will be provided to CPMS from Biostatistics.

9.3 Handling of Missing and Incomplete Data

Subjects may have missing specific data points for a variety of causes. In general, data may be missing due to a subject's early withdrawal from study, a missed visit, or non-evaluability of a specific clinical measurement at its planned clinical visit. Unless specified, no imputation will be used. The general procedures outlined below describe what will be done when a data point is missing.

9.3.1 BMD by DXA

Missing baseline BMD by DXA at any anatomical site will not be imputed. For purposes of the primary efficacy endpoint analysis and secondary efficacy analyses, observed BMD data at month 6 will be used in the ANCOVA models. **Lumbar spine scans at Month 6 will be acquired in duplicate and the average, when both duplicate values are available, will be used. For proximal femur scans, the left side should be used for all scans at all visits. If the right side must be used or is inadvertently used at baseline, then it must be used consistently throughout the study.** Only BMD values collected from the same body site as the baseline BMD will be used for analyses.

9.3.2 Bone Turnover Markers

Missing BTM (either baseline or post-baseline values) and PK data will not be imputed. Any values below the lower limit of quantification will be imputed using the lower limit of quantification for analysis **for BTM and 0 for serum romosozumab concentrations.**

9.3.3 Dates

No imputation will be done on incomplete stop date of an AE or a concomitant medication. The imputation rules for incomplete start dates of AEs or concomitant medications are provided in [Table 1](#). AEs with a partially missing start date that occur prior to Study Day 1 will be considered pre-treatment AEs and excluded from safety analyses. Missing years will not be imputed under any condition. Partial dates will be listed as is on the listings

Table 1. Imputation Rules on Partial Start Date of AE or Concomitant Medication

	Missing	Impute	Exception
Start Date	Day	01	Default to Study Day 1 Date if the event started in the same year and month as Day 1
	Day / Month	01JAN	Default to Study Day 1 Date if the event started in the same year as Day 1

If a death date is incomplete and missing only the day field, it will be imputed as the first day of the month if the latest date from other data is before the month of the death.

However, if the latest date is during the same month as the death, the partial death date will be imputed using the latest date.

For dates of last menstrual period, the imputation rules for partial dates are as follows: if the day is missing, default to day 15; if both month and day are missing, default to July 1st. If the imputed date is on or after the randomization date, default to randomization date minus 1. Missing years will not be imputed under any conditions.

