7.3.10 Concomitant Medications

Concomitant therapies are to be collected in the CRF from the signing of the ICF through the EOS visit. For concomitant therapies affecting bone metabolism, collect therapy name, indication, dose, unit, frequency, start date, and stop date. For all other concomitant therapies, collect therapy name, indication, start date, and stop date.

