7.3.11 Adverse Events, Serious Adverse Events, and Adverse Device Effects

Any serious adverse events occurring after the signing of the ICF through the EOS visit, ET visit, or 30 days after the last dose of IP (whichever period is longer) will be recorded. Any adverse events, adverse device effects, and disease-related events observed by the investigator or reported by the subject occurring after randomization through the EOS visit, ET visit, or 30 days after the last dose of IP (whichever period is longer) will be recorded in the subjects' records and on the appropriate CRFs. Refer to [Section 9.2](#) for more details.

In order to fully evaluate certain events of interest during the study, the following events will be submitted to an independent committee for adjudication:

- potential osteonecrosis of the jaw events
- potential atypical femoral fracture **events**
- **injection site reaction**
- **potential events of serious cardiovascular adverse events**

Further, in order to carefully evaluate cardiovascular events during the trials, all deaths and serious adverse events that are deemed by the investigator to be of potential cardiovascular origin or etiology will be submitted to an independent committee for adjudication, as described in the Clinical Events Classification Charter for Study 20150242. Serious adverse events with terms mapping to a pre-defined preferred term list potentially indicative of cardiovascular etiology will also be adjudicated.

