9.2.2.2 Reporting Procedures for Serious Adverse Events

The investigator is responsible for ensuring that all serious adverse events observed by the investigator or reported by the subject that occur after signing of the informed consent through the EOS visit, ET visit, or 30 days after the last dose of IP (whichever period is longer) are recorded in the subject’s medical record and are submitted to Amgen. All serious adverse events must be submitted to Amgen within 24 hours following the investigator’s knowledge of the event via the Event CRF.

If the electronic data capture (EDC) system is unavailable to the site staff to report the serious adverse event, the information is to be reported to Amgen via an electronic Serious Adverse Event Contingency Report Form within 24 hours of the investigator’s knowledge of the event. See [Appendix B](#) for a sample of the Serious Adverse Event Worksheet/electronic Serious Adverse Event Contingency Report Form. For EDC studies where the first notification of a Serious Adverse Event is reported to Amgen via the eSerious Adverse Event Contingency Report Form, the data must be entered into the EDC system when the system is again available.

The investigator must assess whether the serious adverse event is possibly related to any study-mandated activity or procedure. This relationship is indicated by a “yes” or “no” response to the question: “Is there a reasonable possibility that the event may have been caused by a study activity/procedure?”

The investigator is expected to follow reported serious adverse events until stabilization or reversibility.

In addition to the attributes listed in [Section 9.2.2.1](#), the investigator must also complete the serious adverse event section of the Event CRF.

New information relating to a previously reported serious adverse event must be submitted to Amgen. All new information for serious adverse events must be sent to Amgen within 24 hours following knowledge of the new information. The investigator may be asked to provide additional follow up information, which may include a discharge summary or extracts from the medical record. Information provided about the serious adverse event must be consistent with that recorded on the Event CRF.

If a subject is permanently withdrawn from protocol-required therapies because of a serious adverse event, this information must be submitted to Amgen.

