10.4 Demographic and Baseline Characteristics

Subject demographic and baseline disease characteristics as listed below will be summarized by treatment group based on the FAS defined in [Section 7.1](#).

- demographics (race, sex, ethnicity, age at study entry [year], age groups [<65 , ≥ 65 to <75 , and ≥ 75])
- body composition (height [cm], weight [kg], BMI [kg/m²])
- BMD T-score at lumbar spine, total hip and femoral neck
- BMD (g/cm²) by machine type at lumbar spine, total hip and femoral neck
- bone turnover markers (CTX, P1NP)
- years since menopause (year)
- fracture history (Y/N) (**including historic fracture, historic fracture at age ≥ 45 , historic fracture at age ≥ 55 , time since the most recent fracture in months**)
- laboratory parameters (calcium corrected by albumin, phosphorus, **creatinine, estimated glomerular filtration rate (eGFR), eGFR [< 15 , 15 to < 30 , 30 to < 60 , 60 to < 90 , and ≥ 90 mL/min/1.73m²]**), serum 25 (OH) vitamin D level and iPTH)
- glucocorticoid use (Yes, No)
- substance use in the past 5 years including tobacco use (never, former, current); alcoholic beverages (none, ≤ 2 per day, ≥ 3 per day);
- baseline use of vitamin D (Yes, No)
- baseline use of calcium (Yes, No)
- parental hip fracture (Yes, No, Unknown)
- secondary osteoporosis (Yes, No)
- rheumatoid arthritis (Yes, No)
- **cardiovascular risk factors (age ≥ 75 , < 75], smoking history and other clinical history including hypertension, diabetes, cardiovascular disease, and hypercholesterolemia)**

The cardiovascular risk factors of history of hypertension, diabetes, cardiovascular disease, central nervous system vascular disorder and hypercholesterolemia will be identified based on the Medical & Surgical History eCRF based on MedDRA version 20.0 or later. The SMQ for Hypertension, the SMQ for Hyperglycaemia, and the SOC of Cardiac Disorders and Vascular Disorders will be used to identify preferred terms associated with hypertension, diabetes and cardiovascular disease, respectively. The Dyslipidaemia SMQ will be used to identify history of hypercholesterolemia, excluding terms associated with conditions of low cholesterol or increased high-density lipoprotein. The preferred terms utilized are listed in [Appendix 13.4](#).

Summary tables of prior and concomitant medication will also be generated by treatment group using FAS.

Subject demographic and history of cardiovascular risk factors will be summarized using all subjects in FAS.

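### The SAP's Day 1 default for partial start dates ignores the recorded stop date, so a medication that ended before dosing can be given a start after its stop; for AEs the order of the two date rules is not stated

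*SAP*

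**What the plan says.** SAP 9.3.3 (Dates), Table 1, covers partial start dates of AEs and concomitant medications. A missing day becomes 01; a missing day and month become 01JAN. Each line has one exception:

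- Day missing: "Default to Study Day 1 Date if the event started in the same year and month as Day 1".
- Day and month missing: "Default to Study Day 1 Date if the event started in the same year as Day 1".

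On stop dates the section says only "No imputation will be done on incomplete stop date of an AE or a concomitant medication". For AEs, but not for medications, it adds: "AEs with a partially missing start date that occur prior to Study Day 1 will be considered pre-treatment AEs and excluded from safety analyses". Listings print partial dates as recorded.

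Records that end before dosing can be in the database. Protocol 7.3.10 states: "Concomitant therapies are to be collected in the CRF from the signing of the ICF through the EOS visit". Protocol 7.3.11 records "Any serious adverse events occurring after the signing of the ICF through the EOS visit", and 9.2.2.2 uses the same starting point for reporting ("that occur after signing of the informed consent through the EOS visit"). Screening may take up to 35 days.

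On output, SAP 10.4 says: "Summary tables of prior and concomitant medication will also be generated by treatment group using FAS". It gives no cut-off between prior and concomitant. SAP 10.7.1 tabulates treatment-emergent and serious AEs, and the published SAP shows no date rule for treatment-emergent.

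**The concern.** Defaulting an uncertain start to Day 1 is sensible when the record might have begun on or after dosing. It is not sensible when the recorded stop date shows that the therapy or event was over before dosing. Table 1 makes no such distinction, so it can produce a start later than the stop.

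The gap stands out because two neighbouring rules in SAP 9.3.3 do have a plausibility check. A partial death date is compared with the latest other date for the subject. An imputed last menstrual period that falls on or after randomization is reset to the day before it.

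At stake is the classification of a few records. SAP 6.4 starts the Treatment Period on the first dose date, so a record moved to Day 1 falls inside it. With about 30 subjects per arm, one misplaced SAE would change an arm's incidence by about 1/30 = 3.3 percentage points.

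**Working it through.** The plan states no figure for this rule, so there is none to reproduce. The check applies Table 1 as written.

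**Rule.** Let D be Study Day 1, E the recorded stop date and I the imputed start. If the known month and year (day missing) or the known year (day and month missing) match D, then I = D. Otherwise I is the first day of the known month or year.

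**Consequence.** If the known part matches D and E < D, then I = D > E. The contradiction is certain for every such record.

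**With a stop-date condition.** If E < D, set I to the first day of the known month or year. The true start cannot be earlier than that day and the stop cannot be earlier than the true start, so I ≤ E always.

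**Examples**, with an assumed Day 1 of 20 Mar 2018:

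| Record | Recorded start | Recorded stop | Table 1 start | After stop? | Start with condition |
|---|---|---|---|---|---|
| Medication | Mar 2018 | 10 Mar 2018 | 20 Mar 2018 | yes | 01 Mar 2018 |
| Medication | 2018 | 10 Feb 2018 | 20 Mar 2018 | yes | 01 Jan 2018 |
| Medication | 2017 | 05 Jan 2018 | 01 Jan 2017 | no | 01 Jan 2017 |
| SAE | Mar 2018 | 12 Mar 2018 | 20 Mar 2018 | yes, on Table 1 alone | 01 Mar 2018 |
| SAE | 2018 | 27 Feb 2018 | 20 Mar 2018 | yes, on Table 1 alone | 01 Jan 2018 |
| SAE | Feb 2018 | 27 Feb 2018 | 01 Feb 2018 | no | 01 Feb 2018 |

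**How often the match occurs.** Assume Day 1 on each day of 2018, a start 1 to 35 days earlier, and a fixed duration. Keep only records that ended before Day 1:

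| Assumed duration | Cases | Start after stop, day missing | Start after stop, day and month missing |
|---|---|---|---|
| 1 day | 12,775 | 42.1% | 95.1% |
| 3 days | 12,045 | 38.8% | 94.8% |
| 7 days | 10,585 | 32.5% | 94.2% |
| 14 days | 8,030 | 21.4% | 93.3% |

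With the stop-date condition the count is 0 in every cell. These shares apply only to records that have a partial start, began in those 35 days and ended before Day 1. They are not error rates for the trial.

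**AEs: the two possible orders.** Take the SAE recorded as starting in Mar 2018 and stopping on 12 Mar 2018.

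- Exclusion judged on reported dates: the stop precedes Day 1, so the event is pre-treatment and excluded.
- Table 1 first, exclusion judged on the imputed start: the start is 20 Mar 2018, which is not before Day 1, so the event stays in and has a start after its stop.

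The section does not say which order applies. Medications have no exclusion sentence, so the question does not arise for them and the contradiction stands.

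**The case against.** The strongest reply is that little follows from this rule.

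- **Screening SAEs.** A reader might infer that a resolved screening SAE will be counted as treatment-emergent. The documents do not support that. An SAE with a stop date before Day 1 plainly occurred before Day 1, and the natural reading of the exclusion sentence removes it. What remains is the unstated order.
- **On-treatment medication.** A reader might infer that these medications will be counted as on-treatment. No section classifies medications by imputed start. Stop dates are collected, so a program could classify by them. This objection stands: misclassification is possible, not stated.
- **Prior bone therapy.** A reader might infer that the 5-year bone-therapy history will look like prohibited treatment. Table 1 is titled for AEs and concomitant medication, while that history is collected separately (Protocol 7.3.5), and nothing says that Table 1 governs it. If it did, only starts in Day 1's calendar year would move. With starts assumed uniform over 5 years that is about 182/1,826 = 10%. Eligibility removes much recent use as well, although some short courses remain allowed. Important deviations come from study-team review (SAP 10.3), and nothing ties them to imputed dates.
- **Data quality.** Onset and resolution dates are required for AEs (Protocol 9.2.2.1), and data review queries omissions and discrepancies (12.3). Partial dates may be few.

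None of this removes the core: the rule as written gives an impossible interval for a medication that ended before dosing in the matching month or year, and no other section corrects it.

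**Conclusion.** The point holds in a narrow form and is minor. For medications, Table 1 yields a start after the stop whenever the start is partial, its known part matches Day 1, and the stop precedes Day 1. For AEs, the defect is an unstated order of operations.

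The Day 1 default is an exception to 01 or 01JAN; it would be wrong to read it as applying to every partial start date. Nor should the chance that a record shares Day 1's calendar month or year be read as the size of the error. The error also needs a partial start and a stop before Day 1, and the documents do not say how many such records there will be.

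The reach is descriptive: medication summaries and possibly a few SAE counts. Safety has no planned inferential testing, and no BMD or bone-marker endpoint uses these dates. The conclusion rests on the published SAP, in which part of the appendix is withheld; a definition there could settle the AE question.

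**What to change.** Make two additions to SAP 9.3.3:

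1. In both exceptions of Table 1, apply the Study Day 1 default only if the stop date is missing, ongoing, or not shown (from a complete or partial date) to be before Study Day 1. Otherwise impute 01 or 01JAN.
2. State that the pre-treatment AE exclusion is judged on the reported start and stop dates, before any imputation.

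The cost is two sentences and about one line of code. No additional data are needed and no efficacy analysis changes.
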